#### **Change from Baseline at Week X**

$$= \text{Week X UC-PRO/SS Domain Score} - \text{Baseline UC-PRO/SS Domain Score}$$

A MMRM (Mixed Model Repeated Measures) analysis will be performed to assess the change from baseline in UC-PRO domains at Week X and will include the fixed categorical effects of treatment, visit, study stratification factors, and treatment-by-visit interaction, and the continuous covariates of the baseline continuous UC-PRO domain and baseline UC-PRO domain-by-visit interaction. An unstructured covariance matrix will be used to model the within patient errors within the MMRM.

#### **4.4.2.3.2 Systemic Symptoms Domain**

The systemic symptoms domain collected by the UC-PRO tool ranges from 0-20 with a higher score indicating a worse disease state. Details of the score are in [Appendix 6](#). The scores are summarized using the same methodology used for functional and bowel domain in Section [4.4.2.3.1](#).

#### **4.4.2.4 Inflammatory Bowel Disease Questionnaire**

The IBDQ is a 32-item questionnaire containing four domains: bowel symptoms (10 items), systemic symptoms (5 items), emotional function (12 items), and social function (5 items).

An overall total IBDQ score will be computed by summing the individual 32-item scores. The range for the IBDQ total score is 32–224, with higher scores denoting better health-related quality of life.

The IBDQ questionnaire is administered once per visit as per the study Schedule of Assessments, and is completed by the patient at the clinic.

The change from baseline at Week X in total IBDQ

**Change from Baseline at Week X = Week X IBDQ – Baseline IBDQ**

This is analyzed by an ANCOVA model with the factors used at randomization into the Induction/Maintenance Phases as stratification variables, and the baseline IBDQ score used as a covariate.

#### **4.4.3 Subgroup Analyses**

The following subgroup analyses will be conducted on the primary endpoints for all studies. The subgroup categories are listed in Section 4.3. Study specific subgroups will be included in the study SAPs as required.

The primary endpoints will be summarized by the following subgroups using data collected in the clinical database:

- Baseline MCS
- Disease Location
- Age
- Gender
- Race
- IS use at Baseline
- CS use at Baseline
- Anti-drug antibodies (ADA) –ve/+ve (+ve transient or +ve persistent status)

Additional subgroups analysis will be conducted as appropriate.

### **4.5 PHARMACOKINETIC AND PHARMACODYNAMIC ANALYSES**

#### **Pharmacokinetic Analyses**

Serum concentration at various times during Induction and Maintenance Phases will be listed and summarized by descriptive summary statistics including means, geometric means, ranges, SD, and coefficients of variation.

Individual and mean concentration versus time data will be tabulated and plotted if more than 2 time points are available.

The pharmacokinetic (PK) data from each individual study may be combined with data from other etrolizumab studies to perform a population PK analysis. Population typical value of PK parameters will be estimated for the entire study population, along with estimates of intra- and inter-patient variance and an estimate of random error. Individual patient parameter estimates will be computed using the post hoc analysis procedure. Impacts of covariates on relevant PK parameters will also be evaluated. A separate prospective analysis plan will be prepared, and the population PK analysis will be presented in a separate report for all studies, this will be separate from each study CSR.

### **Pharmacodynamic Analyses**

The pharmacodynamic (PD) biomarker, sMAdCAM-1 absolute concentration and percentage change from baseline values will be listed and summarized by descriptive summary statistics at each time point including but not limited to means, SD, medians, and ranges. Analyses will be split by treatment group and cohort as appropriate.

Additional exploratory PK/PD analyses or modeling may be conducted as appropriate

## **4.6 BIOMARKER ANALYSIS**

Additional biomarker strategies and analyses will be detailed in the Biomarker Analysis Plan.

## **4.7 SAFETY ANALYSES**

The safety populations include all patients who received at least one dose of study drug, and patients will be grouped according to the treatment of the treatment arm they most frequently received. In addition, data will be listed for patients who do not receive the treatment they are assigned to in the safety population at any time point. All safety parameters will be summarized and presented in tables using the safety populations defined for each study. Patients who are not randomized but who receive study drug will be included in the safety population and summarized according to the therapy actually received. The safety data will be listed and summarized at the time of the primary analyses with use of all safety data available at the primary database snapshot. Additional summaries will be run once all patients have completed safety follow-up.

### **4.7.1 Adverse Events**

Adverse events (AEs) will include all terms recorded on the AE Case Report Form (CRF) pages (except pregnancies). For each recorded AE, the term entered by the investigator describing the event (the “reported term”) will be assigned a standardized term (the “preferred term”) and assigned to a superclass term on the basis of the Medical Dictionary for Regulatory Activities (MedDRA) World Health Organization (WHO) dictionary of terms. All analyses of AE data will be performed using the preferred terms unless otherwise specified. For all summary tables, the AEs will be sorted by System Organ Class (in decreasing order of overall incidence) and then by preferred term (in decreasing order of overall incidence). In addition, separate summaries or listings will

be generated for SAEs, deaths, AEs leading to discontinuation of study drug, and adverse events of special interest (AESIs). In addition to summaries or listings, narratives will be provided for all deaths, SAE's, AE's leading to treatment discontinuation and pregnancies as well as for all serious infections, opportunistic infections and malignancies in the individual CSRs.

For the etrolizumab Phase III program, the AESIs (identified by the investigator using the eCRF tick box) are the following:

- Systemic hypersensitivity reactions and anaphylactic and anaphylactoid reaction. These will be further described using the MedDRA anaphylactic reaction SMQ (Standard MedDRA Query) algorithmic and Hypersensitivity SMQ narrow.
- Neurological signs, symptoms, and AEs that may suggest possible progressive multifocal leukoencephalopathy (PML) (see Appendices 5 and 6 of Protocol)
- Suspected transmission of an infectious agent by the study drug
- Cases of potential drug-induced liver injury that include an elevated alanine aminotransferase (ALT) or aspartate aminotransferase (AST) in combination with either an elevated bilirubin or clinical jaundice, as defined by Hy's Law

Specific AEs listed below will also be reported:

- Serious infections (including GI) – Events occurred in the MedDRA Infections and Infestations System Organ Class (SOC) using the primary coding events
- Opportunistic infections – Events occurred in the Sponsor-defined Adverse Event Group Terms
- Malignancies – Events that occur in the MedDRA Malignant and Unspecified Tumours SMQ (narrow).
- Injection site reactions – Events identified using the eCRF tick box indicating an Injection site reaction AND/OR events occurred in the MedDRA Injection Site Reaction High Level Term (HLT) using both primary and secondary coding.

Outputs will be summarized using the safety population split by treatment arm and cohort as appropriate.

Summaries of AEs will be generated to summarize the incidence of treatment-emergent AEs only. Treatment-emergent events are defined as any new AE reported or any worsening of an existing condition on or after the first dose of study drug. If the onset date of the AE is prior to the day of first dose, the AE will be considered treatment-emergent only if the most extreme intensity is greater than the initial intensity (i.e., the intensity for a given AE increases and its end date is on or after the date of the first dose). Non-treatment emergent AE's collected in the database will also be reported separately, for each individual CSRs.

For each treatment group, the incidence count for each AE preferred term will be defined as the number of patients reporting at least one treatment-emergent occurrence of the

event (multiple occurrences of the same AE in one patient will be counted only once). The proportion of patients with an AE will be calculated as the incidence count divided by the total number of patients in the population. Each table will also present the total number of AEs reported where multiple occurrences of the same AE in an individual are counted separately.

The rate per 100 patient years and 95% CIs will be summarized by treatment group for studies (GA28950, GA29102, GA29103, GA28948, and GA28949). Rates will be calculated for AEs, SAEs, and other AE grouping as appropriate. The rate of AEs per 100 patient years is calculated as:

$$= \frac{\text{Total Number of AEs}}{\text{Total Number of Patient Years at Risk}} \times 100$$

All summaries and listings of AEs will be based on the induction safety population or the maintenance safety population and listed in the List of Planned Outputs (LoPO).

#### **4.7.2      Laboratory Data**

Descriptive summaries of laboratory values at baseline and throughout the studies will be summarized by treatment arm.

Change from baseline will be analysed for the following parameters: Hematology (hemoglobin, hematocrit, platelet count, WBC count, lymphocytes, mean corpuscular volume), serum chemistries (sodium, potassium, chloride, bicarbonate, glucose, blood urea nitrogen, creatinine, calcium, total and direct bilirubin, total protein, albumin, alanine aminotransferase, aspartate aminotransferase, alkaline phosphatase), CRP, and fecal calprotectin

Proportion of patients experiencing clinically significant changes relative to baseline will be summarized by treatment arm as appropriate for the parameters listed above.

Laboratory abnormalities and the patient's worst National Cancer Institute Common Terminology Criteria for Adverse Events (NCI CTCAE) grade during study will be summarized by treatment arm as appropriate for parameters listed above.

Elevated liver enzyme tests will be summarized by the following upper limit of normal (ULN) categories as these are indicators of severe liver injury

- ALT or AST >3 × ULN
- ALT or AST >3 × ULN and total bilirubin >2 × ULN as defined by Hy's law:

The number and percentage of patients with positive serum antibodies to etrolizumab (ADA) at baseline (prevalence) and post etrolizumab treatment at any time during the

study (incidence) will be tabulated by treatment arm and listed alongside the primary efficacy outcome.

All summaries and listings of laboratory data will be based on the safety populations and specified in the LoPO.

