3.4.2 Safety Outcome Measures

The safety outcome measures for this study are as follows:

- Incidence and severity of adverse events
- Incidence of serious adverse events
- Incidence and severity of infection-related adverse events
- Incidence of serious infection-related adverse events
- Incidence and severity of injection-site reactions
- Incidence of adverse events leading to study drug discontinuation
- Incidence of laboratory abnormalities
- Incidence of malignancies
- Incidence of ATAs to etrolizumab
- Incidence and severity of hypersensitivity reaction events

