6.5 SAFETY ANALYSES

The safety analyses will include all patients who received at least one dose of study drug in the Induction Phase. Separate summaries of adverse events will be provided for the open-label Induction Phase and the Maintenance Phase.

Safety will be assessed through descriptive summaries of adverse events, laboratory test results (serum chemistry, hematology including complete blood count with differential and platelet counts, and urinalysis), and the incidence of antibodies to etrolizumab.

Additional details will be provided in the SAP.

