Appendix 1 Schedule of Activities (cont.)

- ^c Telephone contact for patients performing home administration: Patients requiring in-clinic drug administration throughout the study will have their study assessments conducted in clinic or via telephone call after their clinic visit at the sites' discretion.
- ^d Unscheduled visit represents a visit that is not per Schedule of Assessments and is required for an adverse event or for potential relapse assessment. All indicated assessments are NOT performed at each unscheduled visit. Assessments would be symptom driven (e.g., only perform PML neurologic examination if patient reports symptoms suspected of PML; for disease worsening, infectious etiologies may be investigated if clinically indicated; and confirmation of clinical relapse is performed by the MCS assessment). Assessments corresponding to items noted in this column should be recorded on the eCRF.
- ^e Perform prior to administration of etrolizumab.
- ^f Serum test at screening for all female patients except those who are more than 1 year postmenopausal or have had a hysterectomy. Urine test at other visits; if urine test result is positive, perform a confirmatory serum test. Pregnancy test will be carried out at home once patient starts etrolizumab administration at home. Patient is to report the pregnancy test via the e-diary. Patients must be instructed at screening and reminded throughout the study that in case of positive pregnancy test they must stop self-administration of study drug and call the site immediately. Do not administer etrolizumab unless the serum pregnancy test result is negative.
- ^g Not required if normal chest X-ray result within 3 months prior to screening.
- ^h Full physical examination required at screening; symptom-driven physical examination at all other timepoints indicated.
- ⁱ PML neurologic examination consists of the PML Subjective Checklist and the PML Objective Checklist. Administer before other assessments, per [Appendix 5](#).
- ^j Not required if unscheduled visit leads to withdrawal and assessment previously conducted at unscheduled visit.
- ^k The following tests are acceptable screening assays for latent TB in this study: purified protein derivative (a tuberculin skin test reaction; e.g., Mantoux test), INF- γ based test (e.g., QuantiFERON[®]-TB Gold).
- ^l Patients must undergo screening for HBV and HCV. This includes testing for HBsAg, anti-HBc, and hepatitis C antibody.

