#### **4.6.3            Laboratory Data**

Details are included in the project SAP, Section 4.7.2.

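### Project SAP 4.7.2 leaves absolute neutrophil count off the closed list that governs change from baseline, clinically significant change and worst CTCAE grade

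*SAP*

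**What the plan says.** Project SAP Section 4.7.2 works in layers.

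- It opens without restriction: "Descriptive summaries of laboratory values at baseline and throughout the studies will be summarized by treatment arm".
- It then says which parameters will be analysed for change from baseline. The hematology part is "Hematology (hemoglobin, hematocrit, platelet count, WBC count, lymphocytes, mean corpuscular volume", followed by serum chemistries, CRP and fecal calprotectin. The list is closed; nothing in it signals that the items are examples.
- Clinically significant change is tied to the same list, where appropriate.
- So is the worst CTCAE grade, which "grade during study will be summarized by treatment arm as appropriate for parameters listed above".
- It ends: "All summaries and listings of laboratory data will be based on the safety populations and specified in the LoPO". LoPO is the List of Planned Outputs.

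Study SAP Section 4.6.3 defers entirely: "Details are included in the project SAP, Section 4.7.2".

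On the protocol side, Section 3.4.2 includes "Incidence of laboratory abnormalities" among the safety outcome measures. Section 6.5 says that the laboratory summaries will cover "hematology including complete blood count with differential and platelet counts, and urinalysis". Section 6.5.2 promises change summaries only for a selection of parameters that it does not name. Section 4.5.1.5 collects absolute neutrophils as part of the differential, and Section 4.1.2 excludes patients with a count below 1500/µL.

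**The concern.** The protocol treats the neutrophil count as important enough to bar entry, and Table 5 (malignancies row) names new or worsening neutropenia first among the blood abnormalities to be evaluated. The SAP then leaves it out of the three summaries that would show whether such abnormalities differ between arms. The summary that matters most is the worst-grade table, because it counts patients by severity from the laboratory values themselves and does not depend on an investigator's decision to report an event.

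What is at stake is completeness of safety reporting for one parameter. Azathioprine, 6-mercaptopurine and methotrexate are permitted as background treatment, and Protocol 1.1 associates these drugs with bone marrow suppression. A neutrophil grade table by arm would therefore be useful even if etrolizumab has no effect on the blood count.

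**Working it through.** There is no sample-size or error-rate figure to reproduce here. The check compares lists.

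**Step 1. Entry limits against the SAP list.** The limits are in Protocol 4.1.2 (laboratory values); the list is in project SAP 4.7.2.

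| Measure with an entry limit | Limit for exclusion | On the SAP list |
|---|---|---|
| Serum creatinine | > 2 × ULN | Yes |
| ALT | > 3 × ULN | Yes |
| AST | > 3 × ULN | Yes |
| Alkaline phosphatase | > 3 × ULN | Yes |
| Total bilirubin | > 2.5 × ULN | Yes |
| Platelets | < 100,000/µL | Yes |
| Hemoglobin | < 8 g/dL | Yes |
| Absolute neutrophils | < 1500/µL | **No** |
| Absolute lymphocytes | < 500/µL | Yes |

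Coverage is 8 of 9. If ALT and AST are counted as one measure it is 7 of 8, and neutrophils is still the only omission.

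**Step 2. Abnormalities that the protocol names.** Of the counts and indices in the Table 5 sentence, anemia maps to hemoglobin, thrombocytopenia to platelets and macrocytosis to mean corpuscular volume, and all three are listed. Neutropenia maps to the neutrophil count, which is not. The sentence also mentions atypical cells, a qualitative finding that a change-from-baseline table would not carry.

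**Step 3. Is this a demand to list everything?** Protocol 4.5.1.5 collects 15 hematology items and the SAP lists 6, so 15 − 6 = 9 are unlisted: red cell count, neutrophils, eosinophils, monocytes, basophils, other cells, mean corpuscular hemoglobin, its concentration, and red cell distribution width. Neutrophils is the only one of the nine with an entry limit.

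**Step 4. What the other planned outputs would show.**

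- Descriptive summaries (Protocol 6.5; opening of project SAP 4.7.2) give neutrophil values by arm. They do not promise a count of patients by grade.
- Adverse event tables are by toxicity grade (Protocol 6.5.1). Under Protocol 5.3.5.4, however, a low count need not be reported if it causes no symptoms, prompts no change in study or concomitant treatment and no intervention, and is not judged clinically significant.
- White cell count is on the list, but a white cell grade is not a neutrophil grade. How far one stands in for the other depends on the rest of the differential, for which the documents give no figures.

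**Step 5. What the added row would contain.** Study SAP 4.6 reports Maintenance safety from the baseline before the first induction dose. Hematology is scheduled at Weeks 10, 20, 44 and 62 after that baseline (Protocol Appendix 1). The Week 10 sample follows open-label etrolizumab in every patient and precedes the first Maintenance dose at Week 12. A worst grade during study, by Maintenance arm, therefore mixes a value obtained under treatment common to both arms with values obtained under randomized treatment.

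**The case against.** The strongest reply is that this is a choice the sponsor was free to make. No section says that a measure with an entry limit must also have a worst-grade table. Protocol 6.5.2 leaves the selection open, and the safety outcome names no parameters. A reader might infer a protocol breach; the text does not support that, and none is claimed.

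A reader might also infer that neutrophil data will go unreported or that neutropenia will be missed. That is not supported either:

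- Neutrophil values are within the planned descriptive summaries.
- Investigators must review all laboratory findings (Protocol 5.3.5.4).
- Serious and opportunistic infections have their own reports (project SAP 4.7.1).
- The independent monitoring committee sees unblinded safety data about every six months (Protocol 3.1.2).

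The selection can also be rationalized. Leukopenia and thrombocytopenia are the protocol's blood-related examples of immunosuppressant toxicity, and lymphocytes fit a drug that acts on lymphocyte trafficking. That is plausible, but neither document gives it as a reason for leaving neutrophils out.

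Finally, the List of Planned Outputs may already contain a neutrophil table. This stands, so the point is confined to what the SAP text plans. The qualifier that the summaries are made as appropriate does not answer it: naturally read, it allows a listed parameter to be dropped, not an unlisted one to be added.

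What survives is narrow: low counts that led to no action and were not judged significant will not be counted by grade and arm under the SAP as written.

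**Conclusion.** The point holds in limited form and is minor. One of nine laboratory measures with an entry limit lacks the three list-bound summaries. The practical loss is a count, by arm, of patients by worst neutrophil grade for a stated safety outcome.

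The weight is small. Neutropenia is not an adverse event of special interest (Protocol 5.2.3), and the nonclinical studies showed no adverse hematologic effect (Protocol 1.2). The documents give no neutropenia rate, so no number of affected patients is claimed.

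The conclusion rests on two readings: that the list in Section 4.7.2 is closed, and that the List of Planned Outputs does not extend it. The second cannot be checked from the protocol and SAP. This is best treated as a nearly free improvement to the plan.

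**What to change.** Add absolute neutrophil count to the hematology list in project SAP Section 4.7.2, or add one line to study SAP Section 4.6.3. Coverage of the entry-limit measures then goes from 8 of 9 to 9 of 9.

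State two things with it. The comparison by arm applies to Maintenance only, since Induction has a single arm. The Maintenance table runs from the baseline before induction, so it includes induction values common to both arms and should be read with that in mind.

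The cost is one more parameter in the list and one more row in tables already planned. No sample, visit or assay is added, because the differential is already collected. If the List of Planned Outputs already has the table, the change only brings the SAP text into line with it.

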#### **4.7.3 Vital Signs**

Vital signs will be summarized using summary statistics and change from baseline proportion of patients experiencing clinically significant changes relative to baseline will be reported if appropriate.

All summaries and listings of vital signs data will be based on safety population and specified in LoPO.

#### **4.7.4 Medical History**

Medical history data collected in the e-CRF will be summarized using summary statistics, reporting the proportion of patients with at least one medical condition and the total number of medical conditions. The medical conditions will then be split out by type.

All summaries and listings of medical history will be based on safety population and specified in the LoPO.

